9.2 Sample Size, Accrual Rate and Study Duration

For the primary outcome, with 73 eligible patients we will have 90% power to detect a correlation coefficient between pre-surgical prone or supine MRI and tumor size of 0.85 from 0.70 with a two-sided one sample z-test at $\alpha=0.05$ level.

With 73 eligible patients, we will also have more than 80% power to detect a difference in correlation from 0.85 between the supine MRI and the pathology tumor size and 0.70 between the standard imaging and the pathology tumor size with a two-sided two sample z-test at $\alpha=0.05$ level, assuming the correlation between the supine MRI and the standard imaging is 0.70.

Assuming the dropout rate will be 10%, we will plan to accrue a total of 80 patients. With an anticipated enrollment of 5 patients per month, accrual should be completed in approximately 16 months.

The below table “Accrual Targets” reflects the accrual targets anticipated for this study. As noted in detail in Section 3.3, men are not likely candidates for breast conserving surgery, and are not eligible for this trial. Approximately 10% of the target enrollment will be Hispanic or African American.

Accrual Targets					
Ethnic Category	Sex/Gender				
	Females	+	Males	=	Total
Hispanic or Latino	8	+	0	=	8
Not Hispanic or Latino	72	+	0	=	72
Ethnic Category: Total of all subjects	80 (A1)	+	0 (B1)	=	80 (C1)
Racial Category					
American Indian or Alaskan Native	1	+	0	=	1
Asian	4	+	0	=	4
Black or African American	12	+	0	=	12
Native Hawaiian or other Pacific Islander	0	+	0	=	
White	63	+	0	=	63
Racial Category: Total of all subjects	80 (A2)	+	0 (B2)	=	80 (C2)

(A1 = A2)

(B1 = B2)

(C1 = C2)

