1.1 Study Design and Hypotheses

This study is designed as a prospective Phase II trial aimed to determine the value of supine breast MRI for women newly diagnosed with stage I-III non-inflammatory breast cancer undergoing upfront surgery or neoadjuvant therapy (NAT).

We hypothesize that breast MRI with supine sequences will provide advanced image-based characteristics for (1) radiological procedures (2) surgical operations and (3) adjuvant radiation delivery, and further hypothesize that these images will allow for superior characterization and localization of breast lesions as compared to traditional imaging studies (mammography, ultrasound, prone MRI). This will be measured by a combination of qualitative (clinician surveys of supine MRI usefulness for radiologic and surgical procedures and for radiation treatment/delivery) and quantitative measures (correlation in residual tumor size estimation with the gold standard method, success rate of US-guided lesion identification and/or biopsy performed with supine MRI guidance, and rate of re-excisions for breast conserving surgical operations when supine MRI used for surgical planning).

More specifically, we hypothesize that:

- (1) Supine breast MRI will provide an accurate assessment of residual breast tumor size
- (2) Supine breast MRI will be superior to other imaging modalities in estimation of final tumor size as determined on post-operative pathology (gold standard).
- (3) Supine MRI will help radiologists identify suspected satellite lesions and/or additional suspicious findings during the second look ultrasound procedure. Tissue sampling under sonographic-guidance is more cost effective and patient centric for the patient compared to biopsy under MRI-guidance; therefore, the correlation of MRI findings with ultrasound findings is an important patient-centered endpoint.
- (4) Supine breast MRI will improve surgical planning efforts for breast conserving surgery by providing surgeons with more accurate information regarding the tumor's location within the breast in the supine position, which will translate into reduced re-excision rates associated with this procedure.
- (5) Supine breast MRI will improve adjuvant radiation therapy planning efforts following breast surgery by providing radiation oncologists with more accurate imaging information of the patient in the supine position, allowing for potentially improved radiation delivery

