A total of 74 patients will be recruited to participate in this study. Enrolled patients will undergo upfront surgery or receive a NAT regimen at the discretion of the treatment team. All patients will have their breast tumor evaluated with standard imaging to include mammography, 2D and/or 3D, ultrasound, prone contrast-enhanced MRI and investigational supine contrast-enhanced MRI sequence pre-surgery. For patients planning for NAT, we will also attempt to obtain a prone contrast-enhanced MRI and investigational supine contrast-enhanced MRI sequence pre-NAT; however if a patient presents with an outside pre NAT MRI this will not be repeated. The tumor's position on all imaging modalities will be registered, and tumor location between supine and prone MRI sequences will be determined. Investigational supine MRI images will be provided to radiologists and surgeons for purposes of performing additional imaging interventions, if they are deemed necessary by the treatment team, and for surgical

planning. Estimates of tumor size pre-operatively as identified by each imaging modality will be compared to final pathology, allowing the correlation of each imaging modality for estimating residual tumor size with the gold standard method (pathology).

For patients undergoing BCT, the prone and supine MRI images will be registered in the image-processing software, 3D Slicer, and the segmented tumor models will be overlaid on the images. Screenshots showing the displacement of the tumor from the prone to the supine images will be provided to the surgeon to plan the tumor resection. Following completion of the operation a survey of the breast surgeon will be administered to determine their perceived usefulness of the supine imaging for surgical planning. Volume of excised tissue, rates of positive margins, and the need for reoperation, will be recorded, and these measures (using supine MRI imaging) will be compared to historical data to determine the impact of supine MRI imaging on surgical outcomes.

Patients requiring postoperative radiation therapy will be referred to radiation oncology post-operatively. Supine MRI images obtained prior to surgery will be provided to the radiation oncologists for breast treatment planning. A survey will then be administered to the attending treating radiation oncologist to assess the usefulness of supine MRI for treatment planning.

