In the upfront surgery setting, the use of Breast MRI has been shown to compliment traditional

imaging modalities (MMG/US) for determining extent of disease; however there remains a problem with over-estimation of lesion size. This combined with the frequency of identification of second lesions which require biopsy (and are often not visible on MMG/US) has been shown to correlate with increased use of mastectomy, with patients often deferring biopsy altogether. Whether or not supine MRI can improve upon correlation with tumor size in the upfront surgery setting and whether or not supine MRI can lead to improved identification of second lesions requiring biopsy has not been tested.

In the NAT setting, breast MRI has demonstrated higher accuracy over physical examination, mammography, and targeted breast ultrasound in the evaluation of tumor response to NAT and prediction of amount of residual disease. [12, 20-28]. The correlation of residual tumor size following NAT and histopathology in patients who underwent prone MRI before BCS has been reported to be approximately $r=0.7$ (Bhattacharyya et al ($r=0.71$), Rosen et al ($r=0.75$), Martincich et al ($r=0.72$), Segara et al ($r=0.75$)[12, 27-29]. For patients who require NAT for downstaging to BCT, repeating the MRI after NAT (pre-surgery) is standard for surgical treatment planning. In practice, it is uncommon to exclusively rely on a single imaging modality for breast cancer evaluation, and newly diagnosed breast cancer patients routinely have diagnostic mammography and ultrasound imaging as well. In patients undergoing NAT, these images are also repeated after NAT (pre-surgery) for surgical treatment planning.

One of the challenges inherent with the current breast MRI design is that the images are obtained with the patient in the prone position. Tumors are displayed to both radiologists and surgeons in relation to their position in the prone breast, however both ultrasound and surgery are performed on the supine breast. The changes in breast position- especially for patients with large or pliable breasts- can significantly displace breast tumors, making it difficult for radiologists to correlate MRI and sonographic findings, and for surgeons to localize tumors intraoperatively[33, 34].

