9.3 Stratification Factors

Not applicable

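### Objective 1 tests one pooled MRI-pathology correlation against a fixed benchmark, but the pool mixes two treatment routes and the only documented value near 0.70 is post-NAT

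*Combined protocol and SAP*

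**What the plan says.** For objective 1, the aim in section 9.2 is this: "detect a correlation coefficient between pre-surgical prone or supine MRI and tumor size of 0.85 from 0.70". The planned test is a one-sample z-test, two-sided, at the 0.05 level. The power claim is "with 73 eligible patients we will have 90% power". The section gives no source for 0.70.

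Section 9.5 plans, for objective 1, a correlation with pathology for prone MRI and another for supine MRI, each with a 95% confidence interval and a one-sample z-test. The null value there is 0.6, not 0.70. Nothing in 9.5 splits objectives 1 or 2 by treatment route. The NAT subgroup analysis and the regression model both belong to objective 3.

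Section 2.1 contains the only correlations near 0.7. Its statement begins "The correlation of residual tumor size following NAT and histopathology in patients who underwent prone MRI before BCS has been reported to be approximately"; the figure given is 0.7, with four studies cited at values of 0.71 to 0.75. For upfront surgery it gives no correlation. It reports that MRI over-estimates lesion size in that setting, and that the effect of supine MRI on size correlation is untested.

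On the population, section 1.1 says: "Enrolled patients will undergo upfront surgery or receive a NAT regimen at the discretion of the treatment team". Section 3.1.5 admits both routes, and no share is planned for either. The first hypothesis in 1.1 reads: "Supine breast MRI will provide an accurate assessment of residual breast tumor size". The section headed "9.3 Stratification Factors" is marked not applicable.

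**The concern.** A Pearson correlation depends on the spread of the measurements as well as on how closely they agree. Pooling untreated tumors with tumors treated by NAT can add between-group spread to MRI size, pathology size or both. The pooled value then reflects case mix as well as imaging performance. A paired comparison largely absorbs this, but a one-sample test against a fixed number does not.

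Two things are at stake for objective 1. A result above the benchmark could partly reflect the mix of routes, and a result at or below it could hide good correlation within each route. Separately, the documented basis for a value near 0.70 describes only one of the two routes, so it is unclear what exceeding it would mean for the pooled population.

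**Working it through.** **The plan's own figure.** Inputs from 9.2: null 0.70, alternative 0.85, n = 73, two-sided alpha 0.05. With Fisher's z:

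- atanh(0.85) - atanh(0.70) = 1.2562 - 0.8673 = 0.3889
- power = Phi(0.3889 x sqrt(70) - 1.96) = Phi(1.29) = 90.2%

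The stated 90% is reproduced; the power calculation is not in error.

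**Effect of pooling.** Let p be the share in one route, r the correlation within each route (equal SDs), and dx, dy the gaps between route means on MRI and pathology, in within-group SDs. With k = p(1-p),

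pooled r = (r + k dx dy) / sqrt[(1 + k dx^2)(1 + k dy^2)].

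For an equal gap d on both axes this is (r + k d^2)/(1 + k d^2). The values of r, p and d are assumptions, because the protocol supplies none of them. With r = 0.70 and p = 0.5 (k = 0.25):

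- d = 0.5: 0.7625/1.0625 = 0.72
- d = 1: 0.95/1.25 = 0.76
- d = 1.5: 1.2625/1.5625 = 0.81

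Two-sided rejection of 0.70 at n = 73, from 40,000 simulated trials per setting, with no within-route gain over 0.70:

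| Gap d (both axes) | 50:50 mix | 30:70 mix | 20:80 mix |
|---|---|---|---|
| 0 | 5% | 5% | 5% |
| 0.5 | 6% | 6% | 6% |
| 1 | 20% | 16% | 12% |
| 1.5 | 60% | 49% | 35% |

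**The other direction.** With a 1 SD gap on one axis only and a 50:50 mix, pooled r = 0.70/sqrt(1.25) = 0.63. If the within-route correlation were 0.85, the same gap would give 0.85/sqrt(1.25) = 0.76, and Fisher-z power against 0.70 would be about 19% instead of 90%.

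**With the null in 9.5.** With within-route r = 0.60, a 50:50 mix and d = 1, pooled r = 0.85/1.25 = 0.68, and 0.6 is rejected in about 22% of trials. The effect does not depend on which null is kept. The choice of null matters in its own right: a true correlation of 0.70 with no pooling effect would be declared different from 0.6 about 31% of the time at n = 73.

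**Stratified test.** Compute Fisher's z within each route, average with weights n-3, and use 73 - 6 = 67 in place of 70. Simulated type I error is 4.7% to 5.2% at every gap and mix tried. Power for 0.85 against 0.70 is Phi(0.3889 x sqrt(67) - 1.96) = Phi(1.22) = 88.9%.

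**NAT stratum alone (assumed sizes).** With 37 patients, Phi(0.3889 x sqrt(34) - 1.96) = 62%. With 22 patients, Phi(0.3889 x sqrt(19) - 1.96) = 40%.

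**Objective 2.** Its assumptions are 0.85 and 0.70, "assuming the correlation between the supine MRI and the standard imaging is 0.70". Power for dependent correlations is 85% to 86% without pooling. With d = 1 and a 50:50 mix the three correlations become 0.88, 0.76 and 0.76, and power is still about 86%.

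**The case against.** The strongest reply is that a pooled, all-comer correlation is what the objectives ask for: sections 1.2 and 9.1 speak of tumor size, not residual tumor size. The gap between routes is also unknown and may be small. All patients must be candidates, or potential candidates, for breast conservation. NAT shrinks large tumors toward that range, and 5.2.2 has post-NAT sizes estimated only when there is no radiographic complete response. At d = 0.5 the error is 6% against 5%, which is negligible. All of this stands as a limit on size. It does not show that the gap is small: section 2.1 also expects pathological complete response in over 50% of some subtypes, and nothing in the plan controls the mix.

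A reader might infer more than the documents support:

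- *That 9.2 took 0.70 from the post-NAT studies.* This is a reasonable inference, since no other source appears, but 9.2 does not say so.
- *That section 9.3 rules out a stratified analysis.* In a single-arm study the entry may only mean that there is no allocation to stratify. The gap is in 9.5.
- *That objective 2 is equally affected.* It is largely protected. Its correlations come from the same patients and move together, and equal correlations stay equal if the modalities share the same mean shift.

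**Conclusion.** The point holds for objective 1 as a cheap improvement. The one-sample test compares a pooled correlation from an uncontrolled mix of routes with a fixed value, and the only documented support for a value near 0.70 comes from one route. Under the stated assumptions the effect is negligible at a gap of 0.5 SD, material from about 1 SD (20% rejection instead of 5% with a 50:50 mix) and large at 1.5 SD (60%). Unequal gaps on the two axes can instead lower the correlation.

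One might conclude that objective 1 will be met through case mix alone. The documents do not support that: they give no size means, SDs or route shares, so neither the size nor the direction of the effect can be stated. The conflict between 0.70 in 9.2 and 0.6 in 9.5 needs resolving whatever the gap turns out to be.

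**What to change.** For objective 1 only:

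- Reconcile the null value between 9.2 and 9.5.
- In 9.5, compute the MRI-pathology correlation within each treatment route, combine by Fisher z with weights n-3 for the one-sample test against the reconciled null, and report the correlation with a 95% confidence interval for each route.
- In 9.2, restate power as about 89% at n = 73 for 0.85 against 0.70. If 0.6 is kept as the null, recalculate the figure.
- State that the documented benchmark comes from post-NAT patients, so a comparison with published prone MRI applies directly only to the NAT stratum. The combined test removes the between-route spread but does not supply an upfront-surgery benchmark. State in advance that the NAT stratum alone has limited power (about 62% with 37 patients, 40% with 22; assumed sizes).

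Objective 2 does not need stratifying.

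The cost is wording plus about one point of power for the combined test (90.2% to 88.9%); 76 evaluable patients would restore 90%. Confidence intervals by route will be wider than the pooled one. Treatment route is known for every patient, so no new data are needed.

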9.3 Stratification Factors

Not applicable

9.4 Interim Monitoring Plan

Not applicable

9.5 Analysis of Primary Endpoints

There are three primary objectives of this study, each with unique endpoints.

The first is to evaluate the correlation between prone breast MRI and pathologic measurement in estimating tumor size, and the correlation between supine breast MRI and pathologic results. A 95% confidence interval will also be calculated for each correlation coefficient. One sample z-test will be conducted to compare whether these correlation coefficients are different from 0.6.

The second is to compare the correlation between supine breast MRI and pathologic measurement for estimation of tumor size, and the correlation between existing breast imaging modalities and pathologic tumor size. Similarly, correlation coefficient will be calculated between supine MRI and the pathologic results and between existing breast imaging modalities and the pathologic tumor size. Two-sample z-test for comparing correlated correlation coefficients will be conducted to compare whether these two correlation coefficients are equal.

The third is to characterize the changes occurring in breast tumor-associated properties/ dimensions between the prone and supine imaging position for all patients with pre-surgical MRIs. We will also determine the correlation of tumor location and geometry on pre-NAT and post-NAT (pre-surgical) supine MRI with prone MRI among the subgroup of patients with pre and post NAT imaging. As described in Section 2.1, in our prior work comparing prone to supine MRI, we utilized image processing software that enabled us to generate tumor models and specifically calculate differences in the metrics computed from the segmented tumor label maps on supine and prone MRI. As a first order statistics, we plan to examine differences in the shape

and size of the tumor on supine and prone MRI. Further, we hope to correlate these difference metrics with variables including but not limited to breast size (measured on the axial slice through the nipple) and location (inner/outer, upper/lower). Correlation coefficients will be calculated for parameters related to tumor shape and size between supine and prone MRI, and one sample t-test (or non-parametric Wilcoxon test) will be used to test whether the difference in shape and size parameters between these two measurements are significantly different from 0. A regression model will be used to check whether these differences are correlated to breast size and location, age and other clinical characteristics.

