9.1 Study Design/Endpoints

The primary objective of the study is to determine the usefulness of pre-surgical prone and supine MRI for estimating tumor size (as compared to tumor size on post-operative pathology, which is the existing gold standard). This will be evaluated using correlation coefficients between estimated tumor size on prone MRI and estimated tumor size on post-operative pathology.

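### The primary one-sample test uses a null correlation of 0.6, but the sample size, stated power and cited benchmark all rest on 0.70

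*Combined protocol and SAP*

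**What the plan says.** Section 9.5 gives the analysis of the first primary objective. Each correlation with pathologic size (prone MRI, supine MRI) is reported with a 95% confidence interval, and "One sample z-test will be conducted to compare whether these correlation coefficients are different from 0.6".

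Section 9.2 describes the design of that test differently: "with 73 eligible patients we will have 90% power to detect a correlation coefficient" of "tumor size of 0.85 from 0.70 with a two-sided one sample z-test", at a two-sided 0.05 level. The power statement for the second primary objective again uses "0.70 between the standard imaging and the pathology tumor size".

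Section 2.1 reports that the correlation of residual tumor size on prone MRI after neoadjuvant therapy with histopathology is about 0.7. The four cited studies give 0.71, 0.75, 0.72 and 0.75.

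Section 9.1 says the primary objective concerns both prone and supine MRI, but its endpoint sentence mentions only one: "This will be evaluated using correlation coefficients between estimated tumor size on prone MRI and estimated tumor size on post-operative pathology".

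**The concern.** One test cannot have two null values. Section 9.5 is the text an analyst will follow, and its null of 0.6 is not the one for which the trial was sized. It appears as a null nowhere else and is given no justification.

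The choice decides what a significant result means. Against 0.70, rejection in the upper direction says that MRI tracks pathologic size better than the performance already cited. Against 0.6, it says only that the correlation exceeds a value that all four cited prone MRI studies already exceeded. A reader who takes the hypothesis from section 9.2 would credit the result with more than it shows. If the conflict is left open, the null could also be settled after the correlations are known.

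**Working it through.** **Inputs.** Null 0.6 (section 9.5); null 0.70, alternative 0.85, n = 73, 90% power, two-sided alpha 0.05 (section 9.2); benchmark 0.7, with individual studies at 0.71 to 0.75 (section 2.1). The document does not name the transformation behind its z-test. I assume Fisher's z, with standard error 1/sqrt(n − 3).

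**Transformed values.** atanh(0.60) = 0.6931; atanh(0.70) = 0.8673; atanh(0.75) = 0.9730; atanh(0.85) = 1.2562. For n = 73, sqrt(70) = 8.3666.

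**Step 1: reproduce the plan's figure.** n = ((1.960 + 1.2816) / (atanh r1 − atanh r0))² + 3.

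- Null 0.70: (3.2416 / 0.3889)² + 3 = 72.5, rounded up to 73. Power at 73 = Phi(0.3889 × 8.3666 − 1.960) = Phi(1.293) = 90.2%. This matches section 9.2. A one-sided 0.05 test would need only 60 patients, so the two-sided version is the one that was used.
- Null 0.60: (3.2416 / 0.5630)² + 3 = 36.1, rounded up to 37. Power at 73 = Phi(0.5630 × 8.3666 − 1.960) = Phi(2.750) = 99.7%. This does not match.

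**Step 2: smallest observed correlation that is significant upward at n = 73.** tanh(atanh r0 + 1.960 / 8.3666).

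- Null 0.60: tanh(0.6931 + 0.2343) = 0.729.
- Null 0.70: tanh(0.8673 + 0.2343) = 0.801.

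An observed value between about 0.73 and 0.80 is therefore significant under section 9.5 and not significant under section 9.2. Two of the four cited studies (both 0.75) fall in that interval.

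**Step 3: probability of a significant upper-side result at n = 73.** Phi((atanh r − atanh r0) × 8.3666 − 1.960). For true r = 0.70 and null 0.60: Phi(0.1742 × 8.3666 − 1.960) = Phi(−0.503) = 30.8%. The other cells follow in the same way.

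| True r | Null 0.60 | Null 0.70 |
|---|---|---|
| 0.70 | 30.8% | 2.5% |
| 0.71 | 36.8% | 3.6% |
| 0.72 | 43.4% | 5.2% |
| 0.75 | 64.8% | 14.1% |
| 0.85 | 99.7% | 90.2% |

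**Step 4: both tests together.** Section 9.5 tests prone and supine MRI separately. I simulated bivariate normal size measurements with both true correlations at 0.70 and an assumed prone–supine correlation of 0.70. At least one of the two tests against 0.6 was significant in about 47% of trials.

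**The case against.** The case on the other side has several fair points.

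- **No success rule.** The protocol sets no go/no-go criterion for the first objective, and hypothesis (1) in section 1.1 claims only accurate assessment. Superiority over existing imaging belongs to the second objective, whose paired test does not use 0.6 and has about 85% to 86% power at n = 73 under the stated assumptions. That objective also means 73 patients is not an excessive number. All this limits the problem to the first objective. It does not tell an analyst which null that objective uses.
- **Prone MRI is the existing standard.** A prone correlation of 0.70 to 0.75 would be expected and would not be a false claim of improvement. The misreading matters most for supine MRI.
- **The 31% is not type I error.** At the written null the error rate stays at 5%, and at a true 0.70 a non-significant result is the likelier one (about 69%). The figure is a false-positive rate only relative to the 0.70 benchmark.
- **The confidence interval helps.** At n = 73 an observed 0.73 has an interval of about 0.60 to 0.82, and 0.80 has about 0.698 to 0.870. A careful reader would see that 0.70 is not excluded. The prespecified test would still be reported as significant.
- **0.6 might have been meant for the mixed population.** The cited 0.7 comes from patients after neoadjuvant therapy, while the trial also enrols patients having upfront surgery. The document does not say this, and if it was the intention, the power statement in section 9.2 describes a different test and is wrong.

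None of these removes the contradiction.

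**Conclusion.** The concern holds. Sections 9.2 and 9.5 give different nulls for the same primary test, and the stated sample size and power come only from 0.70. As written, the test sets its bar at an observed 0.73 where the design implies 0.80. It would be significant with probability 31% to 65% for an MRI correlation in the 0.70 to 0.75 range, compared with 2.5% to 14% for the test that was sized. These figures assume Fisher's z, 73 evaluable patients and approximately bivariate normal sizes. The inconsistency affects the primary inference and should be resolved before analysis. The omission of supine MRI from the endpoint sentence in section 9.1 is a minor drafting fault, since the sentence before it and sections 1.2, 9.2 and 9.5 all include it.

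**What to change.** In section 9.5, replace 0.6 with 0.70 for both the prone and the supine test. State that a claim of better performance requires rejection in the upward direction, which is the same as a lower 95% confidence limit (by Fisher's z) above 0.70. In section 9.1, add supine MRI to the endpoint sentence so that sections 1.2, 9.1 and 9.5 name the same coefficients.

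If 0.6 was deliberate, for example for the mixed upfront-surgery and neoadjuvant population, say why, and correct section 9.2 to the power that null gives (99.7% at n = 73 for 0.85). A significant result should then be described as exceeding 0.6 and not as improving on published MRI.

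The preferred change costs one number and two phrases. It needs no further patients, because 73 already gives 90.2% power against 0.70. The price is a harder test, which is the one section 9.2 planned.
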